## 3. RATIONALE

To enhance the care of patients seen in the primary care setting, Atrium Health has designed a virtual behavioral health integration program. A behavioral health care team comprised of licensed clinicians (Behavioral Health Professionals), health coaches, a consulting psychiatric pharmacist and psychiatric providers follow patients for up to 3 months or more depending on patient need after their primary care office visit. This virtual behavioral health integration (VBHI) program is currently available in 36 Atrium Health primary care practices providing support to over 200 providers and medical residents. The Behavioral health Service line is expanding the program to additional primary care practices. Atrium

Health and the Carolinas Physician Alliance is interested in evaluating the effectiveness of the program on reducing the total cost of care.

Patients may be referred to the VBHI program if they are identified as depressed after administration of the depression screening tool (PHQ-9) or for other concerns by their primary care provider. The primary care provider can request assistance by a real-time in office video assessment or by a telephonic out of office assessment. Patients referred by a provider for ‘other concern’ instead of depression are not included in the evaluation.

For this study, patients who have an elevated PHQ-9 score or report suicidal/homicidal ideation are eligible for analyses and be identified from a behavioral health patient report. Patients meeting eligibility criteria will accrue in both the intervention and usual care arms of the study. At intervention sites, the VBHI program team will reach out to patients utilizing video assessment or telephonic outreach. Patient enrolled in the VBHI program will receive the following core components: Introduction to the patient follow-up process, psychosocial assessment, tracking and treatment recommendations for (residential movement, nutrition, sleep hygiene, stress management, pain management, perinatal/postpartum mood disorders, substance abuse), tracking and treatment recommendations for behavioral health symptoms (depression, anxiety, suicidal ideation, etc.), placement into an appropriate case management program if needed, navigation to additional psychiatric or substance use services if needed, and motivational interviewing and brief therapeutic recommendations if needed.

There may be cases where patients are eligible to enroll in full case management programs based on their insurance and other criteria –in these situations the VBHI team will coordinate a seamless care transition. For example, if a patient has Medicaid through Cardinal Innovations, a managed care organization providing local behavioral health care, and meets certain criteria, the patient would no longer require services from VBHI team as they would be duplicative.

For the primary and secondary objectives, a patient’s contact with the VBHI program ends after 90 days following the primary care office visit, or if there is a failure to contact, or becomes enrolled with a case-management program which provides behavioral health services, or declines services, or dies. The behavioral health care team will ensure the patient is enrolled in a case management program through contact with staff before ending contact with the patient.

This research project is a parallel group, cluster randomized quality improvement evaluation which seeks to evaluate the total cost of care among patients in the VBHI program for up to 90 days after their primary care visit. The outcomes evaluation of this quality improvement intervention has been designed to integrate into the routine care and minimize frontline staff burden by deploying an evaluation in a real-world setting.

## **4. SUBJECT AND SITE SELECTION**

### **4.1. Accrual – Primary Care Practices**

Randomization will occur at the practice level with the primary care practices being identified as an intervention or usual care site for the duration of the study. Out of 20 primary care clinics that have shown interest in the VBHI program, 10 will be randomized into the intervention arm and 10 into the usual care arm. Not all sites in the intervention arm are starting the program immediately. There will be a scheduled rollout of 2-3 clinics per month. As intervention sites come on board, a corresponding control site will begin contributing to the evaluable population. Twelve practices indicated their readiness to incorporate the VBHI program into patient care in 2019 with the remaining indicating 2020. A practice labeled as low volume had historically averaged 15 or less eligible patients per month. A practice labeled as high volume had historically averaged 16 or more eligible patients per month.

Twelve practices were identified by the behavioral health team for a 2019 rollout based on the readiness to engage with the VBHI program in 2019. Practices were clustered by patient volume per month (low n=8, high n=4). The 8 practices with lower volumes were randomly ordered and assigned as either a case or control (1:1). The 4 practices with higher volumes were randomly ordered and assigned as either a case or control (1:1). The six primary care practices and corresponding matched control practice were then randomly ordered for a 2019 rollout. Each month that a practice starts using the VBHI program, patients start accruing from the randomly matched control practice.

Eight practices were identified by the behavioral health team for a 2020 rollout based on the readiness to engage with the VBHI program in 2020. These practices were not ready to engage in 2019. Practices were clustered by patient volume per month (low n=4, high n=4). The 4 practices with lower volumes were randomly ordered and assigned as either a case or control (1:1). The 4 practices with higher volumes were randomly ordered and assigned as either a case or control (1:1). The four primary care practices and corresponding matched control practice were then randomly ordered for a 2020 rollout. Each month that a practice starts using the VBHI program, patients start accruing from the randomly matched control practice.

### **4.2. Accrual – Subjects**

Patients 18 years of age or older at primary care practices with a PHQ-9 overall score  $>10$  or Question 9  $>0$ , and with Medicare or other value-based contract where the VBHI program is offered will be considered exposed to the intervention; whereas, patients seen at sites not utilizing the VBHI program will be considered exposed to usual care. Patients who are in the intervention arm will be treated by the behavioral health care team (licensed clinicians, health coaches, a psychiatric pharmacist and psychiatric providers). Virtual visits are conducted either by video assessment or telephonically. As part of the current care process, all patients with a primary care visit are given the PHQ-2 survey. A score  $\geq 2$  triggers the PHQ-9 survey. Patients who present to participating primary care practices with an elevated patient health questionnaire (PHQ-9) score or report suicide ideation (Question 9) will be

treated and followed per the proposed virtual behavioral health integration (VBHI) program or usual care. Each weekday a list of patients is received by the behavioral health care team. The list includes patients with an elevated PHQ-9 score from the prior day and the associated insurance plan for the patient. The insurance plan is included so that the behavioral health team can target patients with Medicare

or other value-based contracts that report total costs back to Atrium Health. On Mondays, the team receives a list of patients seen between Friday and Sunday.

Patients included in the analysis of this study must meet the inclusion\exclusion criteria and have an insurance claim for the index primary care visit when they became eligible in the enterprise data warehouse (EDW). Patients will begin accruing based on the time the practice goes live according to the role out schedule and will continue for 17 months. The VBHI program is available to any patients in the practice but the evaluation is centered on the cohort of patients meeting the inclusion criteria.

### **4.3. Inclusion\Exclusion Criteria**

#### **4.3.1. Inclusion Criteria**

Eligible patients in the analyses must meet each of the following criteria:

- 18 years of age or older
- Primary care office visit at a selected site based on preventative and outpatient CPT codes
- Have a PHQ-9 and an overall score >10 or Question 9 >0
- Medicare or value-based contract associated with a patient in the past year

#### **4.3.2. Exclusion Criteria**

- A patient will contribute to the analysis once using their initial enrollment to either arm of the study
- No insurance claim for the index primary care visit in the data warehouse upon evaluation

### **4.4. Evaluable Population**

Patients included in the evaluable population for this project, will have their data inform the final outcomes assessment. All patients who meet the inclusion and exclusion criteria in both arms will be assessed for the primary outcome (intent to treat and by per protocol).

## 5. OVERALL DESIGN

### 5.1. Variables

#### 5.1.1. Primary Outcome Variable

The primary outcome variable is total cost of care. A claim for the primary care visit is first identified in the EDW for a patient that meets the inclusion criteria. The total cost of care is defined as the summation of all paid claims  $\leq 90$  days after the primary care visit.

#### 5.1.2. Rates and Variable Descriptions

- a. Demographic characteristics (age, race, gender, insurance plan)
- b. Charlson comorbidity index score

If we determine that we can identify hospital and primary care visits through claims data, we will use that as a source over using just Atrium Health encounters for the utilization rates as specified below.

- c. Patient-centric defined 90-day utilization rate. This is a utilization rate among patients with an ED, inpatient, or observation encounter to any Atrium Health facility ( $\leq 90$  days after the primary care visit).
- d. The 90-day primary care utilization rate. This is a utilization rate among patients with a primary care encounter ( $\leq 90$  days after the primary care visit).
- e. Primary care visit
  - i. At least one CPT code for preventative or outpatient visit
- f. Pharmacy related 90-day total cost of care. The pharmacy total cost of care is defined as the summation of all pharmacy paid claims within 90 days of the primary care visit among patients with pharmacy claim data ( $\leq 90$  days after the primary care visit).

Symptom and health outcomes are assessed at 3, 6, 9, and 12-months among patients who enrolled in the VBHI program.

- g. Asses symptom improvement for depression
  - i. Pre- PHQ-9 score from primary care visit
  - ii. Post- PHQ-9 score
- h. Primary care visit diagnoses (primary or secondary billed diagnoses)
  - i. substance use disorder
  - ii. depression/dysthymia
  - iii. anxiety
- i. Anxiety
  - i. Pre- GAD-7 score from initial enrollment
  - ii. Post- GAD-7 score

- j. Suicidal ideation
  - i. Pre- PHQ-9, Q9 score from primary care visit
  - ii. Post- PHQ-9, Q9 score
- k. Remission of depressive symptoms
  - i. PHQ-9 less than 5 in 2 consecutive months
- l. BMI
  - i. Pre- BMI level from primary care visit
  - ii. Post- BMI level
- m. HbA1c among diabetic patients
  - i. Pre- A1c level from primary care visit
  - ii. Post- A1c level
- n. LDL cholesterol level
  - i. Pre- LDL level from primary care visit
  - ii. Post- LDL level
- o. Hunger vital signs – reported upon enrollment
  - i. Within the past 12 months, we worried whether our food would run out before we got the money to buy more?
  - ii. Within the past 12 months the food we bought just didn't last and we didn't have the money to get more?
- p. Home – reported upon enrollment
  - i. What is your housing situation today?
  - ii. Are you worried about losing your house?
- q. Education – reported upon enrollment
  - i. What is the highest level of school you have finished?
- r. Employment – reported upon enrollment
  - i. What is your current work situation?
- s. Social and emotional health – reported upon enrollment
  - i. How often do you see or talk to people that you care about and feel close to?
  - ii. Stress is when someone feels tense, nervous, anxious, or can't sleep at night because their mind is troubled. How stressed are you?
  - iii. Do you feel physically and emotionally safe where you currently live?
  - iv. In the past year, have you been afraid of your partner or ex-partner?
  - v. In the past year, have you spent more than 2 nights in a row in jail, prison, detention center, or juvenile correctional facility?

## 5.2. Virtual Behavioral Health Integration

The flow of patients from initial contact to their follow-up calls is outlined in Appendix 1. In the existing VBHI primary care workflow, all patients are given the PHQ-2 survey. A score  $\geq 2$  triggers the PHQ-9 survey. The following day the behavioral health team receives a patient report. The report

includes patients seen the prior day at intervention sites that had an elevated PHQ-9 score >10 or reported suicide ideation (Question 9 >0). The Monday report includes patients seen Friday-Sunday. Patients associated with Medicare or other value-based insurance plan are identified in the report. The behavioral health care team will reach out to these patients for enrollment utilizing video assessment or telephonic outreach. The patient always has the option not to be followed by the behavioral health care team.

The behavioral health care team will complete the initial behavioral health assessment. The initial health assessment contains information such as preferred communication method, GAD-7, psychiatry provider, collateral resources, recent ED and hospital utilization, substance use disorder, medication barriers, appointment barriers, community resources, and crisis planning.

The frequency of follow-up assessments depends on the clinical presentation and medication recommendation and/or adherence. The assessment includes information such as a suicide ideation safety screening, an appointment reminder, appointment barrier evaluations, medication reconciliation, medication obtainment follow-up, substance use disorder follow-up, supportive listening, psychoeducation, community resource follow-up, and additional crisis planning.

The Columbia-Suicide Severity Rating Scale (C-SSRS) helps identify whether someone is at risk for suicide, and the severity and immediacy of the risk. It also identifies level of support the person needs. The screening tool is administered during each phone contact to measure suicide ideation. Follow-up patients enrolled in the VBHI program will receive follow-up phone calls. The frequency of calls is dependent on the clinical presentation and medication recommendation and/or adherence. A follow-up assessment is completed upon each phone call.

### 5.3. Usual Care

All patients are given the PHQ-2 survey during the primary care visit. A score  $\geq 2$  triggers the PHQ-9 survey. The PHQ-9 offers providers a concise, self-administrated screening and diagnostic tool for Major Depressive Disorder (Table 1). Treatment can be based on the patients total PHQ-9 score. The patient's provider in the primary care practice has the option to refer the patient to community based behavioral health services, begin medication management within the primary care setting, or encourage the patient to obtain a psychiatric evaluation at the nearest emergency department to assess safety concerns including both suicidal and homicidal ideation. For patients that have a diagnosis of depression or dysthymia, the PHQ-9 is administered every 4 months. There are no follow-up behavioral health services based on the PHQ-9 score once the patient leaves the primary care practice.

PHQ-9 Score	Provisional Diagnosis	Treatment Recommendation
0-4	No Depression	None

5-9	Major Depression, mild	Reassurance and/or supportive counseling Education to call if deteriorates
10-14	Major Depression, moderate	Antidepressant and/or Psychotherapy
15-19	Major Depression, moderately severe	Antidepressant and/or Psychotherapy
≥20	Major Depression, severe	Antidepressant and Psychotherapy

Table 1.  
PHQ-9

scores and standard treatment recommendations

#### 5.4. Patient Graduation from the VBHI Program

- Reached max benefit as deemed by the behavioral health care team
- Depression remission – PHQ-9 <5 for 2 consecutive months
- Unable to connect: 4 calls attempted over 12 days
- Transition to lower level of care
  - Patients who transition to a primary care clinic not utilizing VBHI services
  - Moved out-of-state
  - Discharged from primary care clinic utilizing VBHI services
- Transition to higher level of care
  - Psychiatry/Treatment Program
- Patient states that they are no longer interested in services but their last PHQ-9 >5
- Declined or no longer interested in services
- Death

#### 5.5. Continuation of the Intervention

Patients from participating primary care sites may continue enrolling in the VBHI program after the study period has ended.

### 6. DATA COLLECTION AND REPORTING

Patient demographics, Charlson comorbidity score, and utilization will be obtained from the electronic medical record and billing systems. Data from the initial assessment and follow-up contacts will be stored in HealtheCare, a care management platform in Cerner. Data will be retrieved by an application specialist on the research team. Data may be retrieved retrospective to a patient’s completion of the intervention or usual care arm of the study. A participation rate can be generated from the count of patients enrolled in the VBHI program over the count of patients meeting the inclusion criteria.

A bi-monthly report will be produced for the intervention arm. The report will be by primary care practice and overall showing the prior 2 weeks of activity.

- Count of patients meeting the inclusion criteria
- Count of patients with a HealtheCare account
- Count of patients enrolled in the VBHI program
- Patient list with their enrollment status in HealtheCare

A monthly report will be produced for the intervention arm. The report will be by primary care practice and overall. Report to be generated 2 weeks after the end of the month showing the prior month of activity.

- Count of patients meeting the inclusion criteria
- Count of patients with a HealtheCare account
- Count of patients enrolled in the VBHI program
- Patient list with their enrollment status in HealtheCare

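### No pre-index look-back for cost or acute use is specified in either arm, so the covariate rule for the primary cost outcome has no prior-cost variable to select

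*Combined protocol and SAP*

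**What the plan says.** Section 5.1.1 anchors the primary outcome on the index claim: "A claim for the primary care visit is first identified in the EDW for a patient that meets the inclusion criteria". It then states: "The total cost of care is defined as the summation of all paid claims", counted up to 90 days after that visit. Section 5.1.2 uses the same post-index window for the acute measure ("This is a utilization rate among patients with an ED, inpatient, or observation encounter to any Atrium Health facility"), for primary care use and for pharmacy cost.

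The baseline items that can be had in both arms are "Demographic characteristics (age, race, gender, insurance plan" and "Charlson comorbidity index score", together with the index-visit PHQ-9 and the index diagnoses. On sources, section 6 says: "Patient demographics, Charlson comorbidity score, and utilization will be obtained from the electronic medical record and billing systems". That sentence sets no period, and the section also allows retrospective retrieval.

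The one item on earlier acute use, "recent ED and hospital utilization", belongs to the VBHI team's initial assessment in section 5.2. Section 8.1 lists a visit summary in the same assessment. Section 5.3 describes no counterpart in usual care.

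Section 6.2 fits a linear mixed model with a practice random effect. It adds baseline covariates that correlate strongly with cost or look imbalanced, and names none.

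**The concern.** A patient's earlier cost is usually an obvious candidate predictor of later cost. Here it is not among the defined variables, so the rule in section 6.2 cannot choose it and the baseline table cannot show it.

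This matters more than usual because only 20 practices are randomised, within strata of readiness year and patient volume (section 4.1). Nothing in the allocation balances practices on cost. Ten practices per arm can differ in prior spending by chance, and the listed proxies would show that only indirectly. Two things are at stake: the width of the interval for a highly variable outcome, and the ability to inspect and adjust for the imbalance that the realised allocation produced.

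**Working it through.** **1. Windows, side by side**
- Total cost, acute use, primary care use, pharmacy cost (5.1.1, 5.1.2): all after the index visit.
- Utilization from the record and billing systems (6): no window given.
- Recent ED and hospital use (5.2): before the outcome, but only for patients whom the VBHI team assesses.
- Look-back for cost or acute use in both arms: none in any section.

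**2. Scale.** The documents give no sample size, SD, ICC, alpha or power, so there is no design figure to reproduce. The only reference is in section 6.1: $860.16 per member per year, or 10.8%, from one insurer's evaluation of an embedded, non-virtual programme. It is not declared as the design effect. Spread evenly over the year:
- annual cost = 860.16 / 0.108 = $7,964
- 90-day cost = 7,964 × 90/365 = $1,964
- 90-day saving = 860.16 × 90/365 = $212

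**3. Standard error without prior cost.** With 10 practices per arm and m patients per practice,

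SE = SD × √{(2/10) × [ICC(1 − Rb) + (1 − ICC)(1 − Rw)/m]},

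where Rb and Rw are the shares of between- and within-practice variance that prior cost explains. Assumed for illustration: SD = 2 × mean, ICC = 0.01, m = 200.
- Bracket, no adjustment: 0.01 + 0.99/200 = 0.01495
- SE = 2 × √(0.2 × 0.01495) = 0.109 of the mean, or about $215
- Probability that chance alone gives a difference of $212 or more in either direction: about 0.32

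Over assumed ranges (SD 1.5 to 3 times the mean, ICC 0.005 to 0.05, m 100 to 200) the SE runs from about 7% to 33% of the mean, and that probability from 0.11 to 0.74.

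**4. What adjustment could buy**
- *Equal shares.* If Rb = Rw = r², the interval shrinks by the factor √(1 − r²), whatever the ICC and m. At r = 0.3 this is √0.91 = 0.954; at r = 0.6 it is √0.64 = 0.80. Narrowing is about 5% to 20%.
- *Within-practice only* (Rb = 0, inputs of step 3). Rw = 0.09: bracket 0.01 + 0.00495 × 0.91 = 0.01450, ratio √(0.01450/0.01495) = 0.985. Rw = 0.36: bracket 0.01317, ratio 0.939. Narrowing is about 1.5% to 6%.
- *More between than within.* Rb = 0.50, Rw = 0.25: bracket 0.00871, SE about $164, 24% narrower. Rb = 0.80, Rw = 0.40: bracket 0.00497, SE about $124, 42% narrower.

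With t on 18 df and an assumed two-sided 0.05, power for a 10.8% saving at the step 3 inputs goes from about 15% to 23% (50%/25%) or 37% (80%/40%). The documents fix none of these inputs. They show direction and spread, not a predicted gain.

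**The case against.** Three objections have force.

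First, a reader might infer that prior use and cost are not collected. The documents do not go that far. Section 6 names utilization without a window, from systems covering both arms, and permits retrospective retrieval. What stands is that no look-back is specified; the only defined rates are post-index.

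Second, a reader might infer that a chance cost difference would be mistaken for a programme effect, or that the comparison is biased. Practices are randomised within strata, and the practice random effect puts between-practice variation into the standard error. The unadjusted comparison is therefore not systematically biased by the missing covariate. Nor is baseline risk wholly unmeasured: the proxies exist, and section 6.2 provides for balance checks and added covariates. What stands is narrower. A wider interval does not show or correct the imbalance in the allocation actually drawn, and the proxies do not measure spending.

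Third, a look-back may be less simple than it sounds. Section 5.1.2 leaves open whether hospital visits can be identified in claims, pharmacy cost exists only for some patients, and section 6.1 says the cost measure is still being built. The eligibility condition, "Medicare or value-based contract associated with a patient in the past year", does not guarantee a full year of coverage. These are real limits on the fix, and they shape it. They do not remove the gap. Equally, adjustment would not by itself make the trial well powered for a 10.8% saving under the step 3 inputs.

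**Conclusion.** The point holds as a worthwhile improvement to make before analysis, not as a threat to validity. No section defines a pre-index window for cost or acute use in either arm, and the only record of earlier use is specific to VBHI. The rule in section 6.2 therefore has no prior-cost variable to select. The loss is precision and the ability to see and adjust for chance imbalance among 10 versus 10 practices.

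The size cannot be fixed from the documents. The 5% to 20% narrowing rests on an assumed pre-post correlation of 0.3 to 0.6 and on equal explained shares between and within practices. Other assumed splits give anything from about 1.5% to 42%.

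**What to change.** In sections 5.1.2 and 6, define for both arms:
- total paid claims in a fixed look-back, for example the 365 days before the index visit with the index day excluded, from the same EDW claims source as the outcome, with days of contract coverage in that window;
- any ED, inpatient or observation use in the window, from claims if these can be identified and otherwise from Atrium encounters, using the same source as the outcome measure;
- pharmacy paid claims in the window, where pharmacy claims exist.

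Report these by arm in the baseline table. In section 6.2, prespecify pre-index total cost as a fixed covariate in the primary model, outside the data-driven rule. Use a form that is defined at zero, such as log(cost + 1) plus a zero-cost indicator, and add an indicator for incomplete look-back. Do not use the VBHI assessment item as a baseline, since usual care has no equivalent.

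Cost: mainly an additional date range in the claims extract, provided earlier claims are held for these patients, which the sponsor should confirm. No patient contact, visit or eligibility rule changes. Downside: patients new to a contract have a short look-back, and the coverage indicator does not recover their missing cost.

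### Patients enter the primary cost population through a PHQ-9 completed after practices know their arm, and no by-arm check of screening is planned, so differential case-finding could bias the cost comparison in either direction.

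*Combined protocol and SAP*

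**What the plan says.** Section 4.1 fixes the arm first: allocation is by practice, and each practice keeps its arm throughout. Of the 20 practices, "10 will be randomized into the intervention arm and 10 into the usual care arm". Patients come later: "Each month that a practice starts using the VBHI program, patients start accruing from the randomly matched control practice", and section 4.2 adds "Patients will begin accruing based on the time the practice goes live". Section 4.3.1 makes the PHQ-9 an entry criterion: "Have a PHQ-9 and an overall score >10 or Question 9 >0". Under section 4.4, everyone in either arm who meets the criteria is assessed for the primary outcome.

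Sections 4.2, 5.2 and 5.3 describe the same screening rule for both arms: a PHQ-2 for every patient, with a score of 2 or more triggering the PHQ-9. What follows a qualifying score differs. Section 5.2 describes a next-day report that "includes patients seen the prior day at intervention sites that had an elevated PHQ-9 score >10 or reported suicide ideation", from which the team contacts patients with Medicare or a value-based plan. Section 5.3 leaves referral, medication or emergency evaluation to the usual-care provider, with no behavioral health follow-up driven by the score once the patient has left the practice.

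Section 6 schedules two reports that count eligible patients: "A bi-monthly report will be produced for the intervention arm" (covering two weeks of activity) and "A monthly report will be produced for the intervention arm". Neither counts visits, PHQ-2s or PHQ-9s. Section 6.2 analyses patients by the assignment of their practice, tests baseline balance, and adds covariates that prove imbalanced or strongly correlated with cost.

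**The concern.** In a cluster trial, intention-to-treat by practice keeps each included patient in the right arm. It does not protect the step that decides who is included, when that step comes after randomisation and the arm can influence it. Here staff at a live VBHI practice know that a completed PHQ-9 brings help for the patient, so going live could raise PHQ-2 or PHQ-9 completion there. The two arms would then hold different kinds of patient before any treatment effect.

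The primary outcome is a mean cost, so a shift in case mix moves it directly. Cheaper extra patients would look like a saving; costlier ones would hide a real saving. The planned baseline variables are not well placed to reveal this. Section 5.1.2 lists the index PHQ-9 only under symptom measures for VBHI enrollees, records the social determinants at enrollment, and does not list prior cost.

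**Working it through.** **No design figure to reproduce.** Section 6.1 gives no sample size, power, standard deviation, intracluster correlation or eligibility rate. Its one quantitative anchor is a cited saving of $860.16 per member per year, or 10.8%.

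**Scale.** If 10.8% is relative to the comparator, the implied annual cost is 860.16 / 0.108 = $7,964. Over 90 days this is 7,964 × 90/365 = $1,964, and the cited saving is 860.16 × 90/365 = $212.

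**Size of the artefact.** Suppose VBHI practices find a fraction *f* of extra eligible patients whose mean cost is *r* times that of the other patients, and VBHI has no effect. The arm mean becomes (1 + f·r)/(1 + f) times its former value, so

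apparent saving = f(1 − r)/(1 + f).

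Both *f* and *r* are assumptions; the documents give neither.

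| f | r | Calculation | Apparent change |
|---|---|---|---|
| 10% | 0.8 | 0.10 × 0.20 / 1.10 | 1.8% saving |
| 20% | 0.7 | 0.20 × 0.30 / 1.20 | 5.0% saving ($98 per 90 days) |
| 30% | 0.6 | 0.30 × 0.40 / 1.30 | 9.2% saving |
| 20% | 1.5 | 0.20 × (−0.50) / 1.20 | 8.3% excess ($164 per 90 days) |

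The savings in the first three rows are between 1.8/10.8 = 17% and 9.2/10.8 = 85% of the cited figure. To reproduce the whole 10.8%, solve f = 0.108/(1 − r − 0.108): 28% extra patients at r = 0.5, or 56% at r = 0.7. At r = 0.9 no amount of extra case-finding is enough.

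**Would a comparison of eligible counts reveal it?** Take a 28% excess (0.276 before rounding), 10 practices per arm, two-sided 5%, and an assumed between-practice SD of log eligible rates. The standard error is SD × √(2/10) and the difference is ln(1.276) = 0.244.

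| SD of log rate | Power (normal approximation) |
|---|---|
| 0.2 | 0.78 |
| 0.3 | 0.44 |
| 0.4 | 0.28 |
| 0.5 | 0.19 |

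The normal approximation is slightly generous with 20 practices: a t-test on 18 degrees of freedom gives 0.73 in the first row and 0.18 in the last. A non-significant difference in counts would therefore give little reassurance.

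**The case against.** The strongest reply is that the plan already limits the problem. The PHQ-2 is given to everyone as existing care, a fixed score triggers the PHQ-9, and section 5.3 describes the PHQ-9 as completed by the patient. Usual-care providers also have their own reasons to use the score. If the rule is followed equally, there is no bias, and nothing in the documents shows that it is not. This stands as a real safeguard, but an unchecked one: staff still decide in practice whether the form is handed out.

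From the one-armed reports a reader might infer that eligibility is ascertained only at VBHI practices, so that a difference could never be seen or corrected. The documents do not support that. Section 3 has eligible patients accruing in both arms, section 4.4 analyses them all, and section 6 allows retrospective retrieval for the usual care arm, so control counts will exist at analysis. Section 4.1 refers to historical monthly volumes, section 10.3 provides for enrollment review as needed without naming an arm, and section 6.2 plans balance tests and adjustment. The section 6 reports are mainly programme-operations reports: three of their four items concern care-management accounts or programme enrollment.

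These points give partial detection. They do not supply the missing denominators. A higher eligible count may mean more visits, more screening or more illness, and a count alone cannot say which. The named balance tests also ignore clustering.

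**Conclusion.** The concern holds as a gap in checking, not as evidence that bias has occurred. Entry follows allocation, a qualifying score has different consequences by arm, and no by-arm record of screening completion is planned. Index PHQ-9 for both arms and prior cost, the variables most likely to show a case-mix shift, are not listed for comparison or adjustment.

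The size is unknown. Under the assumed inputs it runs from a 1.8-9.2% spurious saving to an 8.3% spurious excess, before any covariate adjustment, against a cited saving of 10.8%. A reader might infer that the bias must favour VBHI because extra patients would be milder. That does not follow: they must still score above 10 or report suicidal ideation, and the documents give no costs for them. That practices are unblinded is inferred from the design, though safely, since VBHI sites run the programme.

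**What to change.** 1. **Section 6.** For all 20 practices, extract from the electronic medical record, by month and before and after go-live: visits by adults with Medicare or a value-based contract, PHQ-2s done, PHQ-9s done, and patients meeting the criteria. Tabulate by arm beside the primary result, and judge differences by their size, not by a significance test.
2. **Section 6.2.** Compare index PHQ-9 and pre-index cost between arms, and name both in advance as covariates in the primary model.
3. **Section 6.2.** Add a supportive sensitivity analysis of 90-day cost in adults with Medicare or a value-based contract who had a billed depression/dysthymia, anxiety or substance use diagnosis in the 12 months before their practice pair's go-live. Index each at the first visit after go-live, whether or not a PHQ-9 was completed. Index PHQ-9 will be missing for some of them, so this model should not depend on it.

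The cost is extra queries on existing systems and one more model, with no site work. The sensitivity population includes patients never offered outreach and leaves out newly identified ones, so its estimate is diluted. It should inform interpretation and not override the primary result.
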